Appendix 1: Glossary of Abbreviations

Abbreviation	Full Term
AE	Adverse event
AESI	Adverse Events of Special Interest
ALT	Alanine Aminotransferase
ARAS	All randomized analysis set
AST	Aspartate Aminotransferase
ATC	Anatomic Therapeutic Classification
CBC	Complete Blood Count
CO2	Carbon Dioxide
CP	Conditional Power
CRF	Case Report Form
CSR	Clinical Study Report
CTCAE	Common Terminology Criteria for Adverse Events
DMC	Data Monitoring Committee
DRF	Death or Respiratory Failure
ECG	Electrocardiogram
FES	Full Efficacy Set
FSS	Full Safety Set
HR	Hazard Ratio
IBW	Ideal Body Weight
iNO	Inhaled Nitric Oxide
IP	Investigational Product
ITT	Intention-to-treat
LFT	Liver Function Test
LDH	Lactate Dehydrogenase
MedDRA	Medical Dictionary for Regulatory Activities
MetHb	Methemoglobin
NIAID	National Institute of Allergy and Infectious Diseases
PaO2	Partial Pressure of Oxygen
PPAS	Per Protocol Analysis Set
PT	Preferred Term
RT-PCR	Reverse transcription polymerase chain reaction
SAP	Statistical Analysis Plan

SAE	Serious Adverse Event
SOC	System Organ Class
SpO2	Oxygen Saturation
TEAE	Treatment Emergent Adverse Event
TEG	Thrombelastography

Appendix 2: Imputation for Partial or Missing Dates

Partial or missing dates will only be imputed for AEs and concomitant medications, not for any other dates. If dates are missing or incomplete for an AE (including deaths) or concomitant medication, the following algorithm will be used for imputation:

Table 5: Imputation Rules for Partial or Missing Start Dates

Start Date		Stop Date						
		Complete: yyyymmdd		Partial: yyyymm		Partial: yyyy		missing
<1 st dose	≥1 st dose	<1 st dose	≥1 st dose	yyyymm	yyyy	yyyymm	yyyy	
		1	n/a	1	n/a	1	1	1
Partial: yyyymm	≠ 1 st dose yyyymm	2	2	2	2	2	2	2
		1	3	1	n/a	1	1	1
Partial: yyyy	≠ 1 st dose yyyy	3	3	3	3	3	3	3
		4	1	4	1	4	1	1
1 = Impute the date of first dose 2 = Impute the first of the month 3 = Impute January 1 of the year 4 = Impute January 1 of the stop year								

Note: If the start date imputation leads to a start date that is after the stop date, then do not impute the start date.

Imputation rules for partial or missing stop dates:

1. Initial imputation
 - a. For partial stop date "mmyyyy", impute the last of the month.
 - b. For partial stop date "yyyy", impute December 31 of the year.
 - c. For completely missing stop date, do not impute.
2. If the stop date imputation leads to a stop date that is after the death date, then impute the stop date as the death date.
3. If the stop date imputation leads to a stop date that is before the start date, then there is a data error and do not impute the stop date (i.e. set the stop date as missing).

Imputation rules for partial or missing death dates:

1. If death year and month are available but day is missing:
 - a. If "mmyyyy" for last contact date = "mmyyyy" for death date, set death date to the day after the last contact date.
 - b. If "mmyyyy" for last contact date < "mmyyyy" for death date, set death date to the first day of the death month.
 - c. If "mmyyyy" for last contact date > "mmyyyy" for death date, data error and do not impute.
2. If both month and day are missing for death date or a death date is totally missing, set death date to the day after the last contact date.

The imputed dates will be used to assess whether AEs should be considered as treatment-emergent and if concomitant medications should be included in the safety summaries, however the original, partial dates will be included in data listings.

Appendix 3: Abnormal Values for Selected Laboratory Parameters

Abnormal values for selected parameters will be graded by the central laboratory using criteria based on CTCAE Version 5.0.

Appendix 4: Tables, Figures, and Listings

Table Number	Title	Population
Table 14.1.1.1	Subject Analysis Sets	All Randomized Analysis Set
Table 14.1.1.2	Enrollment by Center	All Enrolled Subjects
Table 14.1.1.3	Subject Disposition	Full Efficacy Set
Table 14.1.1.5.1	Important Protocol Deviations	All Randomized Analysis Set
Table 14.1.1.5.2	Important Protocol Deviations	Full Efficacy Set
Table 14.1.2.1	Demographic Characteristics	All Randomized Analysis Set
Table 14.1.2.2	Demographic Characteristics	Full Safety Set
Table 14.1.2.3	Demographic Characteristics	Full Efficacy Set
Table 14.1.2.4	Demographic Characteristics	Per Protocol Analysis Set
Table 14.1.3.1	Medical History by System Organ Class and Preferred Term	All Randomized Analysis Set
Table 14.1.3.2	Medical History by System Organ Class and Preferred Term	Full Safety Set
Table 14.1.3.3	Medical History by System Organ Class and Preferred Term	Full Efficacy Set
Table 14.1.3.4	Medical History by System Organ Class and Preferred Term	Per Protocol Analysis Set
Table 14.1.4.1	Prior Medications by ATC Classification and WHO Drug Dictionary Preferred Term	Full Efficacy Set
Table 14.1.4.2	Prior Medications by WHO Drug Dictionary Preferred Term	Per Protocol Analysis Set
Table 14.1.5.1	Concomitant Medications by WHO Drug Dictionary Preferred Term	Full Efficacy Set
Table 14.1.5.2	Concomitant Medications by WHO Drug Dictionary Preferred Term	Per Protocol Analysis Set
Table 14.2.1.1	Analysis of Patients who Died or had Respiratory Failure	All Randomized Analysis Set
Table 14.2.1.1.1	Analysis of Patients who Died or had Respiratory Failure by Race	All Randomized Analysis Set
Table 14.2.1.1.2	Analysis of Patients who Died or had Respiratory Failure by Gender	All Randomized Analysis Set
Table 14.2.1.1.3	Analysis of Patients who Died or had Respiratory Failure by Age Group	All Randomized Analysis Set
Table 14.2.1.1.4	Analysis of Patients who Died or had Respiratory Failure by Baseline Oxygen Level	All Randomized Analysis Set
Table 14.2.1.1.5	Analysis of Patients who Died or had Respiratory Failure by No. of Co-Morbidities	All Randomized Analysis Set
Table 14.2.1.2	Analysis of Patients who Died or had Respiratory Failure	Per Protocol Analysis Set
Table 14.2.1.3	Logistic Regression Analysis of Patients who Died or had Respiratory Failure (DFR)	All Randomized Analysis Set
Table 14.2.1.4	Logistic Regression Analysis of Patients who Died or had Respiratory Failure (DFR)	Per Protocol Analysis Set
Table 14.2.1.5	Tipping Point Analysis of Logistic Regression Model	All Randomized Analysis Set

Table Number	Title	Population
Table 14.2.1.6	Tipping Point Analysis of Logistic Regression Model	Per Protocol Analysis Set
Table 14.2.2.1	Summary of NIAID Score by Time Point	All Randomized Analysis Set
Table 14.2.2.1.1	Summary of NIAID Score by Time Point Within Race	All Randomized Analysis Set
Table 14.2.2.1.2	Summary of NIAID Score by Time Point Within Gender	All Randomized Analysis Set
Table 14.2.2.1.3	Summary of NIAID Score by Time Point Within Age Group	All Randomized Analysis Set
Table 14.2.2.1.4	Summary of NIAID Score by Time Point Within Baseline Oxygen Level	All Randomized Analysis Set
Table 14.2.2.1.5	Summary of NIAID Score by Time Point Within No. of Co-Morbidities	All Randomized Analysis Set
Table 14.2.2.2	Mixed Effects Repeated Measures Model of NIAID Score	All Randomized Analysis Set
Table 14.2.2.3	Summary of Subject Recovery	All Randomized Analysis Set
Table 14.2.2.3.1	Summary of Subject Recovery by Race	All Randomized Analysis Set
Table 14.2.2.3.2	Summary of Subject Recovery by Gender	All Randomized Analysis Set
Table 14.2.2.3.3	Summary of Subject Recovery by Age Group	All Randomized Analysis Set
Table 14.2.2.3.4	Summary of Subject Recovery by Baseline Oxygen Level	All Randomized Analysis Set
Table 14.2.2.3.5	Summary of Subject Recovery by No. of Co-Morbidities	All Randomized Analysis Set
Table 14.2.2.4	Summary of Subject Hospital Discharge	All Randomized Analysis Set
Table 14.2.2.4.1	Summary of Subject Hospital Discharge by Race	All Randomized Analysis Set
Table 14.2.2.4.2	Summary of Subject Hospital Discharge by Gender	All Randomized Analysis Set
Table 14.2.2.4.3	Summary of Subject Hospital Discharge by Age Group	All Randomized Analysis Set
Table 14.2.2.4.4	Summary of Subject Hospital Discharge by Baseline Oxygen Level	All Randomized Analysis Set
Table 14.2.2.4.5	Summary of Subject Hospital Discharge by No. of Co-Morbidities	All Randomized Analysis Set
Table 14.2.2.5	Summary and Analysis of Hospital Duration	All Randomized Analysis Set
Table 14.2.2.5.1	Summary and Analysis of Hospital Duration by Race	All Randomized Analysis Set
Table 14.2.2.5.2	Summary and Analysis of Hospital Duration by Gender	All Randomized Analysis Set
Table 14.2.2.5.3	Summary and Analysis of Hospital Duration by Age Group	All Randomized Analysis Set
Table 14.2.2.5.4	Summary and Analysis of Hospital Duration by Baseline Oxygen Level	All Randomized Analysis Set
Table 14.2.2.5.5	Summary and Analysis of Hospital Duration by No. of Co-Morbidities	All Randomized Analysis Set
Table 14.2.2.6	All-Cause Mortality	All Randomized Analysis Set
Table 14.2.2.6.1	All-Cause Mortality by Race	All Randomized Analysis Set
Table 14.2.2.6.2	All-Cause Mortality by Gender	All Randomized Analysis Set
Table 14.2.2.6.3	All-Cause Mortality by Age Group	All Randomized Analysis Set
Table 14.2.2.6.4	All-Cause Mortality by Baseline Oxygen Level	All Randomized Analysis Set
Table 14.2.2.6.5	All-Cause Mortality by No. of Co-Morbidities	All Randomized Analysis Set

Table Number	Title	Population
Table 14.2.2.7	Disease-Specific Mortality	All Randomized Analysis Set
Table 14.2.2.7.1	Disease-Specific Mortality by Race	All Randomized Analysis Set
Table 14.2.2.7.2	Disease-Specific Mortality by Gender	All Randomized Analysis Set
Table 14.2.2.7.3	Disease-Specific Mortality by Age Group	All Randomized Analysis Set
Table 14.2.2.7.4	Disease-Specific Mortality by Baseline Oxygen Level	All Randomized Analysis Set
Table 14.2.2.7.5	Disease-Specific Mortality by No. of Co-Morbidities	All Randomized Analysis Set
Table 14.2.2.8	Summary of RT-PCR Results by Time Point	All Randomized Analysis Set
Table 14.2.2.8.1	Summary of RT-PCR Results by Time Point by Race	All Randomized Analysis Set
Table 14.2.2.8.2	Summary of RT-PCR Results by Time Point by Gender	All Randomized Analysis Set
Table 14.2.2.8.3	Summary of RT-PCR Results by Time Point by Age Group	All Randomized Analysis Set
Table 14.2.2.8.4	Summary of RT-PCR Results by Time Point by Baseline Oxygen Level	All Randomized Analysis Set
Table 14.2.2.8.5	Summary of RT-PCR Results by Time Point by No. of Co-Morbidities	All Randomized Analysis Set
Table 14.2.2.9	Difference in Proportion in RT-PCR Results at Discharge by Treatment Group	All Randomized Analysis Set
Table 14.3.1.1	Summary of Exposure	Full Efficacy Set
Table 14.3.2.1	Overall Summary of Treatment-Emergent Adverse Events	Full Safety Set
Table 14.3.2.2	Treatment-Emergent Adverse Events by System Organ Class and Preferred Term	Full Safety Set
Table 14.3.2.3	Serious Treatment-Emergent Adverse Events by System Organ Class and Preferred Term	Full Safety Set
Table 14.3.2.4	Treatment-Emergent Adverse Events Leading to Discontinuation of IP by System Organ Class and Preferred Term	Full Safety Set
Table 14.3.2.5	Treatment-Emergent Adverse Events with Outcome of Death by System Organ Class and Preferred Term	Full Safety Set
Table 14.3.2.6	Treatment-Emergent Adverse Events by System Organ Class, Preferred Term, and Relationship to IP	Full Safety Set
Table 14.3.2.7	Treatment-Emergent Adverse Events by System Organ Class, Preferred Term, and Maximum Severity	Full Safety Set
Table 14.3.2.8	Subjects with Adverse Events with Outcome of Death	Full Safety Set
Table 14.3.2.9	Subjects Who Experienced Serious Adverse Events	Full Safety Set
Table 14.3.3.1.1	Hematology Results by Time Point	Full Safety Set
Table 14.3.3.1.2	Biochemistry Results by Time Point – Chemistry	Full Safety Set
Table 14.3.3.1.3	Biochemistry Results by Time Point – Liver Function Tests	Full Safety Set
Table 14.3.3.1.4	Biochemistry Results by Time Point – Lipid/Protein Panel	Full Safety Set
Table 14.3.3.1.5	Biochemistry Results by Time Point – Factors/Other Proteins	Full Safety Set

Table Number	Title	Population
Table 14.3.4.1	Vital Sign Results by Time Point	Full Safety Set
Table 14.3.5.1	Electrocardiogram Results	Full Safety Set
Table 14.3.6	Physical Examination by Time Point	Full Safety Set
Figure 14.2.1.1	Forest Plot of Frequent Adverse Events	Full Safety Set
Listing 16.1.7	Randomization Assignments	All Randomized Analysis Set
Listing 16.2.1.1	Discontinued Subjects	All Randomized Analysis Set
Listing 16.2.1.2	Discontinuation of Investigational Product (IP)	All Randomized Analysis Set
Listing 16.2.2	Protocol Deviations	All Randomized Analysis Set
Listing 16.2.3.1	Subject Analysis Sets	All Screened Subjects
Listing 16.2.4.1	Demographic and Baseline Data	All Randomized Analysis Set
Listing 16.2.4.2	General Medical History	All Randomized Analysis Set
Listing 16.2.4.3	Prior and Concomitant Medications	All Randomized Analysis Set
Listing 16.2.5.1	Administration of Investigational Product – INO Pulse Usage	All Randomized Analysis Set
Listing 16.2.5.3	Treatment Compliance	All Randomized Analysis Set
Listing 16.2.6.1	NIAID Score Results	All Randomized Analysis Set
Listing 16.2.7.1	Treatment-Emergent Adverse Events	All Randomized Analysis Set
Listing 16.2.7.2	Non treatment-Emergent Adverse Events	All Randomized Analysis Set
Listing 16.2.7.3	Death Details	All Randomized Analysis Set
Listing 16.2.8.1	Hematology Results and Change from Baseline	Full Safety Set
Listing 16.2.8.2	Biochemistry Results and Change from Baseline	Full Safety Set
Listing 16.2.8.5	Pregnancy Test Results (Females of Childbearing Potential only)	Full Safety Set
Listing 16.2.9	Vital Signs	Full Safety Set
Listing 16.2.10	CT Scan Results	Full Safety Set
Listing 16.2.11	X-Ray Results	Full Safety Set
Listing 16.2.12	Methemoglobin Results	Full Safety Set
Listing 16.2.13	Electrocardiogram Results	Full Safety Set
Listing 16.2.14	Physical Examinations	Full Safety Set

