subject can be continued on INOpulse pending the repeat results. If the repeat RT-PCR results come back negative, the subject should be discontinued from INOpulse therapy. If the subject deteriorates after discontinuation of INOpulse, the Investigator should consider the reintroduction of INOpulse therapy

²Vital signs measured twice daily from Baseline until the last dose of INOpulse. Vital signs include heart rate, respiratory rate, blood pressure, and temperature. In the event an increase in O₂ flow rate is clinically indicated, SpO₂ should be monitored every 6 hours until stabilized. Document oxygen flow requirements.

³Methemoglobin assessed via Masimo RAD-57 (provided by Sponsor). Methemoglobin should be < 3% and SpO₂ >89% (with supplemental O₂ required) prior to continuing with treatment and should be monitored prior to, during the 1st hour (every ½ hour) and approximately 4-5 hours after initiation of INOpulse therapy. Thereafter, methemoglobin should be assessed twice daily (in conjunction with study drug cartridge changes) and remain ≤ 7 %. Otherwise, study drug should be discontinued.

⁴Chest x-ray or CT scan following onset of symptoms within 14 days prior to randomization and any time prior to discharge, as clinically indicated.

⁵Subjects will receive iNO125 mcg/kg IBW/hr or placebo for 24 hrs daily (until resolution of hypoxemia, protocol defined respiratory failure, discharge or Day 28 whichever occurs first.. In instances where continuous INOpulse dosing is not feasible (eg, due to PPE limitations), INOpulse should be used a minimum of 12 hours daily.

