11.2 Full Safety Set

The Full Safety Set (FSS) includes all randomized subjects who received any amount of study drug. This is the primary analysis set for safety analyses.

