11.3 Full Efficacy Set

The Full Efficacy Set (FES) includes all randomized, COVID-confirmed subjects who received any amount of study drug. Note that subjects who began study treatment with high suspicion of COVID infection but subsequently had negative test results on the RT-PCR swab – will be excluded from FES.

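### The only exposure and disposition summary tables are set on the Full Efficacy Set, so exposure omits some treated subjects and disposition omits some randomised ones

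*SAP*

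**What the plan says.** In SAP Appendix 4, Table 14.3.1.1, "Summary of Exposure", and Table 14.1.1.3, "Subject Disposition", both carry the Full Efficacy Set in the population column. They are the only exposure and disposition summary tables in the list.

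SAP 11.3 says the FES "includes all randomized, COVID-confirmed subjects who received any amount of study drug", and it expressly removes "subjects who began study treatment with high suspicion of COVID infection but subsequently had negative test results on the RT-PCR swab". SAP 11.2 says the FSS "includes all randomized subjects who received any amount of study drug. This is the primary analysis set for safety analyses". Table 14.3.2.1, "Overall Summary of Treatment-Emergent Adverse Events", and all later tables in the 14.3 series are on the FSS.

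The protocol (synopsis screening list and Table 2, footnote 1) lets a subject be randomised with RT-PCR pending and stay on INOpulse while a repeat swab is awaited. It then says: "If the repeat RT-PCR results come back negative, the subject should be discontinued from INOpulse therapy".

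SAP 13.1 promises counts by arm of subjects who complete or leave the study, with reasons. SAP 13.3.1 defines hours and days of exposure and says they will be listed. Neither section names a population for these outputs that would override Appendix 4. SAP 13.5 and 13.5.1 put the primary analysis on all randomised subjects, whether or not study drug was stopped.

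**The concern.** An exposure table should describe the same people as the safety tables it sits beside. Here, a subject dosed on suspicion and later found negative contributes adverse events, laboratory values and vital signs to the FSS tables but no hours or days to the exposure summary. The protocol itself creates this group by allowing randomisation before the swab result is known.

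A disposition table should account for everyone randomised, above all when the primary analysis includes everyone randomised. On the FES it starts from subjects who were both dosed and confirmed. A subject randomised and never treated, or treated and then found negative, does not enter it. A reader of the primary result needs to know by arm how many subjects did not receive, or stopped, study drug and why, and the planned summary tables do not give this.

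**Working it through.** The plan states no figure on this point, so there is none to reproduce. The check compares set definitions with table labels and then sizes the gap.

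**Step 1: how the sets nest** (SAP 11.1 to 11.3)
- ARAS = all randomised.
- FSS = randomised and dosed.
- FES = randomised, dosed and COVID-confirmed.
- So FES ⊆ FSS ⊆ ARAS. FSS − FES = dosed but not confirmed. ARAS − FSS = never dosed.

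**Step 2: labels against purpose** (SAP Appendix 4)

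| Output | Set assigned | Who is left out |
|---|---|---|
| Disposition, 14.1.1.3 | FES | never dosed; dosed but not confirmed |
| Exposure, 14.3.1.1 | FES | dosed but not confirmed |
| All other 14.3 tables | FSS | never dosed (appropriate for safety) |
| Primary analysis, 14.2.1.1 and 14.2.1.3 | ARAS | nobody |

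Table 14.3.1.1 is the one exception in its series. Demographics and medical history are planned on all four sets, and important deviations on both the ARAS and the FES. Disposition has no ARAS version and exposure has no FSS version.

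**Step 3: size of the exposure gap**

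Missing from exposure = N dosed × f, where f is the share of dosed subjects not confirmed. N = 500 is the target in SAP 8.1; that all 500 are dosed is assumed. The documents give no value for f, so a range is used:

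- f = 2%: 500 × 0.02 = 10 missing, FES = 490
- f = 5%: 500 × 0.05 = 25 missing, FES = 475
- f = 10%: 500 × 0.10 = 50 missing, FES = 450

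With exposure on the FSS, the difference from the adverse-event tables is 0 by definition. The disposition table is short by the same number plus the never-dosed, for whom the documents also give no rate.

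**Step 4: would relabelling disposition show the RT-PCR stops?** Not by itself. SAP 13.1 tabulates leaving the study. The protocol rule stops INOpulse, while follow-up continues for 30 days after the last dose (Protocol 9.2 and the early-discontinuation footnote to Table 2). Such a subject may well complete the study. Table 14.3.2.4 does summarise study-drug stops, but only those caused by adverse events.

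**The case against.** The strongest reply is that this is a labelling matter in two descriptive tables, with the information available elsewhere. Much of that stands.

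A reader might infer that the RT-PCR-negative and never-dosed subjects go uncounted, or that an imbalance between arms is hidden. The documents do not support this. Table 14.1.1.1 reports set membership, and Tables 14.1.2.1 to 14.1.2.4 give demographics by arm with sample sizes on the ARAS, FSS, FES and PPAS. Subtraction within each arm then yields both groups. Listings 16.2.1.1, 16.2.1.2 and 16.2.5.1 are on the ARAS and show the individual subjects. What is missing is a summary of drug stops by reason and arm.

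A reader might also infer that adverse-event results are distorted. They are not. SAP 13.6.2 plans counts, percentages and odds ratios, with no exposure-adjusted rate, and Table 14.3.1.1 supplies no denominator to any of them.

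Finally, one might put a percentage on overstated exposure. With f of 5% to 10%, 4 days for confirmed subjects and 1 to 3 days for negatives, mean FSS exposure is (1 − f) × 4 + f × d, which runs from 0.90 × 4 + 0.10 × 1 = 3.70 to 0.95 × 4 + 0.05 × 3 = 3.95 days. The FES figure of 4.0 would then be 1% to 8% too high. These inputs are not in the documents in usable form. The 4 days is an expanded-access median, from a programme that also admitted suspected cases. No duration is given for negatives, the repeat swab is optional, and INOpulse may be reintroduced. Shorter exposure in this group is plausible but not established, even in direction.

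What remains is that neither table describes the population its purpose requires, and nothing in the SAP text corrects this.

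**Conclusion.** The point holds as an inconsistency in two reported tables. Followed as written, the plan gives an exposure summary that omits treated subjects and a disposition table that omits randomised subjects. The exposure gap is 10, 25 or 50 of 500 at an assumed 2%, 5% or 10% dosed but unconfirmed, if all 500 are dosed. It is zero only if every dosed subject is confirmed. No adverse-event percentage, hypothesis test, error rate or primary estimate changes. The case for acting is that the correction is cheap and that the only adverse-event-independent account of drug stops would otherwise be a listing.

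**What to change.** 1. In SAP Appendix 4, change the population of Table 14.3.1.1 to the Full Safety Set and of Table 14.1.1.3 to the All Randomized Analysis Set.
2. In SAP 13.1 and Table 14.1.1.3, add by arm the number never dosed and the number who stopped study drug, with reasons, including a repeat negative RT-PCR. Keep these rows separate from leaving the study. The label change alone would not deliver them.
3. In SAP 13.3.1, state that hours and days of exposure are summarised by arm on the FSS as well as listed.

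FES versions of both tables may be kept as supplements. The cost is two labels, a sentence or two in each of 13.1 and 13.3.1, and a few table rows. No new data are needed: Listings 16.2.1.2 and 16.2.5.1 already draw on drug discontinuation and usage for all randomised subjects.
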